**Investigator Name:**

**Investigator's Signature:**

**Date**

**SYNOPSIS**

Sponsor	Tarsius Pharma, Ltd.
Study Title	A Phase I/IIa randomized, double masked, dose-ranging study to evaluate the safety and tolerability of TRS01 eye drops in subjects with active non-infectious anterior uveitis.
Study Objective	The primary objective of the study is to investigate the safety and tolerability of TRS01 [REDACTED] and [REDACTED] (w/v) eye drops in subjects with active non-infectious anterior uveitis.
Study Population	The study population will consist of male and female subjects, aged 18 or older, with active non-infectious anterior uveitis requiring initiation of additional topical steroid treatment.
Number of Subjects	Up to 20 subjects that meet the selection criteria will be randomized for treatment in one study eye.
Study eye	The study eye will be identified based on the severity of Anterior Chamber Cells (ACC) at Day 1. The eye with the most severe inflammation (higher ACC grade) will be selected as the study eye. If the ACC score is the same in both eyes, the right eye (OD) will be identified as the study eye. If the fellow eye has concurrent active uveitis at Day 1 or at any time during the study, the investigator can treat the subject's fellow eye per the standard of care. Only the study eye of each subject will be treated with IP.
Investigational Product	TRS01 [REDACTED] and [REDACTED] eye drops will be supplied as investigational product (IP).
Route and duration of administration	Study subjects will administer the randomly assigned treatment four times a day (QID) for 4 weeks.
Study Design	
This is a Phase I/IIa randomized, double masked, dose-ranging study designed to evaluate the safety and tolerability of TRS01 eye drops ([REDACTED] in subjects with active non-infectious anterior uveitis).
 
Potential study participants will be required to sign an informed consent document and meet all inclusion/exclusion criteria.
 
Eligible subjects will be randomized to treatment as follows:
 
 
[REDACTED]
 
 
Once it is determined that all eligibility criteria have been met, subjects will be enrolled and treated with one of two concentrations of TRS01 in a 1:1 ratio. Up to 20 eligible subjects will be enrolled at approximately

Safety and Tolerability Outcomes	
Assessment of both systemic and ocular adverse events. AEs will be captured by verbatim term and coded using MedDRA.
 
Relevant clinical findings will also be recorded in the electronic case report form (eCRF) related to the following:
 
 
1. BCVA using ETDRS
 
2. Slit-lamp biomicroscopy, specifically evaluation of intraocular anterior inflammation
 
3. IOP measurement
 
4. Dilated ophthalmoscopy
 
5. Safety parameters of interest include a change from baseline to each visit in ocular signs such as corneal/conjunctival tolerability and IOP measurements.
 

Exploratory Efficacy Measurements	
 
• Anterior chamber cell count by slit-lamp biomicroscopy and by anterior chamber SD-OCT in selected sites.
 
• Anterior chamber flare assessed on slit-lamp biomicroscopy
 
• Change in macular edema by macular OCT
 
• Subject-rated ocular pain assessment
 

Eligibility Criteria	
Inclusion Criteria
 
Individuals of either gender or any race will be eligible for study participation if they are:
 
 
1) 18 years of age or older
 
2) Able to provide informed consent, follow instructions and complete all required study visits for the duration of the study.
 
3) Diagnosed with active non-infectious anterior uveitis requiring an increase or initiation of topical steroids for management of ocular inflammation.
 
 
An eligible subject must have:
 
[REDACTED]
 
[REDACTED]
 
[REDACTED]
 
[REDACTED]
 
[REDACTED]
 
[REDACTED]
 
[REDACTED]
 
[REDACTED]
 
[REDACTED]

- 5) Use adequate birth control by men and women, if of reproductive potential and sexually active. Adequate birth control is defined as agreement to consistently practice an effective and accepted method of contraception throughout the duration of the study and for 2 weeks after the last study visit.
  - a) For females of childbearing potential, adequate birth control methods will be defined as hormonal contraceptives, intrauterine device or double barrier contraception, i.e., condom + diaphragm, condom or diaphragm + spermicidal gel or foam.
  - b) For males, adequate birth control methods will be defined as double barrier contraception, i.e., condom + diaphragm, condom or diaphragm + spermicidal gel or foam.
  - c) For postmenopausal females, menopause is defined as one year without menses; if in question, a follicle-stimulating hormone of  $>40$  IU/L must be documented. Hysterectomy, bilateral oophorectomy, or bilateral tubal ligation must be documented, as applicable.

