## 1 INTRODUCTION

Uveitis refers to a broad spectrum of ocular inflammatory diseases which are associated with both systemic infectious and non-infectious conditions. Non-infectious uveitis, a potentially blinding condition that is the fifth leading cause of visual loss in the developed world (third leading cause of preventable blindness), has been estimated to account for 10% of all visual impairment in the western world and 10–15% of cases of total blindness [Nussenblatt, 1990; Merida et al., 2015].

The inflammation associated with uveitis affects the uvea of the eye (iris, ciliary body and choroid) and it is characterized by an inflammatory process that may be acute, recurrent, chronic or acute-on-chronic. Untreated, recurrent bouts of uveitis eventually lead to tissue destruction from direct inflammation or from complications such as cataract, glaucoma and macular edema. Clinically, uveitis manifestations include pain, blurry vision, conjunctival hyperemia, anterior chamber cells, anterior chamber flare, fibrin deposition and corneal endothelial inflammatory precipitates.

Uveitis may affect either the anterior or the posterior segment or in the case of panuveitis, it affects the entire eye. Anterior uveitis, which specifically refers to uveitis in the anterior segment of the eye, is the most common and accounts for approximately 80% of non-infectious uveitis cases in the United States [Thorne et al., 2016].

The present clinical trial evaluates the treatment of non-infectious anterior uveitis with TRS01.

Topical corticosteroids represent first line treatment for both non-infectious anterior uveitis and postoperative inflammation [Kim et al., 2019]. The side effects associated with steroid use significantly limit prolonged treatment. The most common adverse effects of ocular steroids are cataract and elevated intraocular pressure (IOP) which can lead to steroid related glaucoma.

Given the limitations of steroid treatment, there is an unmet medical need for an effective anti-inflammatory drug that does not have an IOP-elevating effect or cause the formation of cataracts. Tarsius Pharma, Ltd. has developed a novel therapeutic approach for local prevention and treatment of ophthalmic inflammatory diseases. [REDACTED]

TRS is the active drug substance of TRS01 which is an [REDACTED] drug product candidate developed for topical ocular administration (eye drops). Pre-clinical studies have demonstrated the safety and tolerability of TRS01.

[REDACTED]

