### 7.2 SAFETY VARIABLES

Safety measures include AEs/SAEs and clinical assessments from the slit-lamp biomicroscopy findings, IOP, and dilated ophthalmoscopy findings.

AEs and ocular safety measures to be collected in this study are listed in [Table 3](#).

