**TABLE 3: OCULAR SAFETY MEASURES**

Safety Measure	Note
Slit-lamp biomicroscopy: Lid hyperemia, lid edema, conjunctival hyperemia, chemosis, corneal edema, conjunctival discharge/exudate	The status of each of these biomicroscopy parameters will be rated as 0 = None, 1 = Mild, 2 = Moderate, or 3 = Severe. For each abnormal record, the clinical significance (Clinically Significant or Not Clinically Significant) will also be determined. Slit-lamp biomicroscopy will be performed at all study visits.
Intraocular pressure	The IOP measurements will be performed by Goldmann applanation tonometry with a single measurement. IOP pressure recorded in mmHg (e.g., 18 mmHg). IOP measurements will be performed at all study visits,
Dilated Ophthalmoscopy: Vitreous haze, retina vessels, macula, optic nerve, cup/disc ratio.	The status of the macula, vessels and optic nerve will be determined as Normal or Abnormal. The cup/disc ratio will be recorded with two decimal points (e.g., 0.80). Dilated ophthalmoscopy will be performed at all visits.
BCVA	The visual acuity test is used via a standardized ETDRS chart.

These ocular safety measures will be summarized using descriptive statistics. For continuous ocular safety measures, changes from Baseline (Day 1/Visit 1) variables will also be summarized descriptively. Safety parameters of interest include a change from baseline to each visit in ocular signs such as corneal/conjunctival tolerability, IOP measurements.

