### 8.1 EFFICACY VARIABLES

Efficacy of TRS01 will be assessed by evaluation of anterior chamber inflammation by Investigator assessment with slit-lamp biomicroscopy, and may also be assessed by anterior chamber SD-OCT automated quantification of anterior chamber cells at select sites.

Slit-lamp biomicroscopy of both eyes will be used to examine eye structures at each study visit. At Day1/Visit 1 (Screening/Randomization), slit-lamp biomicroscopy will be performed prior to IP administration. Areas assessed will include lids/lashes, conjunctiva, cornea, anterior chamber cells and flare, iris, pupil, lens.

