#### 9.1.3 Analysis of Efficacy

Efficacy measures will be ACC and flare.

Both Investigator-rated ACC and flare data will be assessed as a change from baseline (Visit 1/Day 1) Weeks 1 through 4 and a descriptive comparison of the two active treatment groups will be performed.

If available, anterior chamber SD-OCT cell data will be assessed as a change from baseline (Visit 1/Day 1) on Weeks 1 through 4 and a descriptive comparison of the two active treatment groups will be performed.

Changes in subject-rated ocular pain assessment on Weeks 1 through 4 will be evaluated via a descriptive comparison between the two active treatment groups.

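### The synopsis makes anterior chamber inflammation a safety outcome, but no specified table counts the study eyes whose cells or flare rise above baseline

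*Combined protocol and SAP*

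**What the plan says.** The synopsis lists, as item 2 of its safety and tolerability outcomes, "Slit-lamp biomicroscopy, specifically evaluation of intraocular anterior inflammation". Its next row gives, as exploratory efficacy, "Anterior chamber cell count by slit-lamp biomicroscopy and by anterior chamber SD-OCT in selected sites", followed by slit-lamp flare. The same examination therefore has both roles.

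The body of the protocol carries the two roles forward unequally:

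- **Section 3.1** keeps slit-lamp biomicroscopy as a safety item but drops the reference to intraocular inflammation.
- **Section 7.2** states "AEs and ocular safety measures to be collected in this study are listed in" Table 3. The slit-lamp row of that table reads "Lid hyperemia, lid edema, conjunctival hyperemia, chemosis, corneal edema, conjunctival discharge/exudate". ACC, flare and lens are not in it.
- **Section 8.1** describes a wider examination: "Areas assessed will include lids/lashes, conjunctiva, cornea, anterior chamber cells and flare, iris, pupil, lens".
- **Section 9.1.2** says that slit-lamp assessments are summarized as safety, without saying which ones.
- **Section 9.1.3** says "Efficacy measures will be ACC and flare", taken as change from baseline at Weeks 1 to 4 and compared descriptively between the two active groups. It names no statistic.
- **Appendix 1** schedules slit-lamp examination at every visit, including Weeks 7 and 10.

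**The concern.** Safety and tolerability is the primary objective. In an inflammatory eye disease, more inflammation in the treated eye is a central harm to look for, and the synopsis names it as such. Yet ACC and flare have an explicit analysis only as efficacy, which is built to describe average benefit rather than to count eyes that got worse.

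Three further gaps add to this.

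- Section 7.3 puts events readily accounted for by the uveitis itself under Unrelated. Section 9.1.2 tabulates treatment-related adverse events but only lists treatment-emergent ones. A flare-up during treatment could therefore be missing from the adverse event table.
- The explicit analysis of ACC and flare stops at Week 4, so inflammation returning after dosing ends is examined but has no named summary.
- Section 6.2 keeps rescued subjects in the study to Visit 7. Section 9 gives no rule for ACC or flare recorded after rescue.

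The lens is a secondary instance. The Introduction describes the unmet need as an "effective anti-inflammatory drug that does not have an IOP-elevating effect or cause the formation of cataracts", and the lens is examined at each visit, but Table 3 does not include it.

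**Working it through.** The plan has no figure to reproduce: Section 9.2 gives no formal basis for the sample size and the comparison is descriptive. The check is mainly a reading of the text, with arithmetic for scale.

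**Step 1. Which text governs the safety summary of the slit-lamp examination?**

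- Narrow reading: 7.2 points to Table 3, and the commitment under that table to summarize attaches to its list. ACC, flare and lens are then outside the safety summary.
- Broad reading: 9.1.2 covers slit-lamp assessments without restriction, and 8.1 includes cells, flare and lens in that examination. They are then inside it.

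Both readings are possible, so two programmers could produce different safety tables. Under neither reading does the plan define worsening of ACC or flare, or call for a count of eyes above baseline.

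**Step 2. Would the general rules in 9.1 supply the count?**

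Continuous measures get mean, SD, median, minimum and maximum. Categorical measures get number and percent. If grades are tabulated as categories at each visit, the table does not link an eye to its own baseline. Only a tabulation of the change itself would, and none is specified. If change is treated as continuous, the following applies.

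**Step 3. Illustration.** Up to 20 subjects (9.2) at 1:1 (3.3) gives 20/2 = 10 eyes per arm. The patterns of change below are assumptions; the documents give none.

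- Arm A, eight eyes improve one grade and two worsen one grade: mean = (8 x (-1) + 2 x 1)/10 = -0.6; median -1; SD = sqrt((8 x 0.16 + 2 x 2.56)/9) = sqrt(6.4/9) = 0.84; maximum +1.
- Arm B, six improve one grade and four are unchanged: mean = (6 x (-1) + 4 x 0)/10 = -0.6; median -1; SD = sqrt((6 x 0.16 + 4 x 0.36)/9) = sqrt(2.4/9) = 0.52; maximum 0.

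Mean and median are identical, although two eyes worsened in A and none in B. Even four of 10 worsening by one grade, with six improving, gives mean (-6 + 4)/10 = -0.2 and median -1. The maximum separates A from B, but shows only that at least one eye worsened. If changes could take only the values -1, 0 and +1, a reader could solve for the count from n, mean and SD (three equations, three unknowns). With more possible values that no longer works in general.

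**Step 4. What a count would say.** Clopper-Pearson 95% limits for x of n are the 0.025 quantile of Beta(x, n-x+1) and the 0.975 quantile of Beta(x+1, n-x).

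| Eyes worse | 95% CI |
|---|---|
| 0/10 | 0 to 30.8% |
| 1/10 | 0.3 to 44.5% |
| 2/10 | 2.5 to 55.6% |
| 3/10 | 6.7 to 65.2% |
| 0/20 (both doses) | 0 to 16.8% |

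The chance of at least one worsened eye among 10 is 1 - (1 - p)^10. For assumed true rates p of 5%, 10%, 20% and 30% it is 40%, 65%, 89% and 97%. The count is therefore imprecise, but informative for rates of 20% or more.

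**The case against.** A reader might infer that the plan excludes intraocular inflammation from safety, or that worsening eyes will be visible only as a smaller average benefit. The documents do not support either.

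- Table 3 is not confined to external signs. Its ophthalmoscopy row lists "Vitreous haze, retina vessels, macula, optic nerve, cup/disc ratio", and other rows cover IOP and BCVA. The accurate statement is that the slit-lamp row omits ACC, flare and lens.
- Section 9.1.3 does not prescribe a mean. Graded data could fall under the number-and-percent rule, and if they do not, minimum and maximum are planned. Section 9.1 also lists all data by treatment, subject and visit, which is readable with up to 20 subjects.
- The broad reading of 9.1.2 with 8.1 would put ACC, flare and lens in the safety summary at all visits.
- The synopsis item sits under a commitment to record findings, and they are recorded.
- A clinically important flare-up or new cataract could be reported as an adverse event. Rescue use is recorded, and one rescue criterion is redacted, so its coverage of ACC cannot be judged.
- The protocol defers detail to a Statistical Analysis Plan; the statistical text available here is Section 9, so a table of change in grade may be planned elsewhere.

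All of this stands as a limit on the point. None of it supplies a specified count of eyes above baseline, and the adverse event route is weakened by the causality definition and by tabulating only treatment-related events.

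**Conclusion.** The point holds as a gap between the synopsis and the specified safety analysis. The synopsis makes anterior chamber inflammation a safety outcome; Table 3 does not carry it; 9.1.2 is ambiguous; and the only explicit analysis of ACC and flare is as efficacy through Week 4. The information would exist in listings, so the risk is an incomplete safety summary rather than lost data.

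The consequence cannot be sized from the documents, which give no worsening rate and no threshold. The eight-and-two example (mean -0.6; 2 of 10, 95% CI 2.5 to 55.6%) is illustration only. Both arms receive active drug and there is no control, so even a good count stays descriptive and cannot separate a drug effect from the course of the disease. The lens omission is real but secondary. The change is worth making because safety is the primary objective and the cost is small. The conclusion assumes that no separate analysis plan already contains such a table.

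**What to change.** 1. Reconcile the synopsis, Section 3.1, Table 3 and Section 9.1.2 by adding ACC and flare to the slit-lamp safety measures, with lens as a secondary item.
2. In 9.1.2, specify a table by dose and visit, through Week 10, giving the number and percent of study eyes with ACC or flare above the baseline grade, and separately any new or worse lens finding.
3. Identify rescued eyes in that table, and state how values recorded after rescue are shown.
4. Have the sponsor define, before unmasking, the size of increase that counts as worsening.
5. Keep the 9.1.3 efficacy summaries as they are.

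The cost is protocol and analysis plan wording plus one or two tables. Every item is already examined at each scheduled visit, so no procedure is added.

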## Exclusion Criteria

In order for a subject to be eligible they may not:

	

• Have any form of infectious uveitis.

• Have active retinitis.

• Have cancer or melanoma that is actively treated with immunotherapy.

• Be pregnant or lactating.

• Have been treated with intravitreal or periocular steroids in the study eye within 90 days of Visit 1 or for the duration of the study (including but not limited to Iluvien, Retisert, Ozurdex, etc.).

• Have been treated with any intravitreal injection within 30 days prior Visit 1 or for the duration of the study.

• Require treatment with any systemic steroids greater than 10 mg/day.

• Require topical ocular therapy with steroids more than twice a day (BID) in the study eye. Note: up to 3 additional drops of topical steroids within 7 days prior to Visit 1 is permitted.

• Be diagnosed with Fuchs Corneal Dystrophy.

• Use any topical ophthalmic medications other than those allowed in the study.

• Have any significant ocular disease in addition to the uveitis that may confound the trial results per the Investigator's judgement.

• In the opinion of the Investigator, have current clinically significant dry eye requiring therapy of greater than twice a day (BID) eye drops in the study eye. Use of PRN artificial tears up to twice a day is allowed and should not be dosed within 10 minutes of investigational product dosing.

• Use any Cannabidiol products during the trial.

• [REDACTED], narrow angle glaucoma, or glaucoma treated with more than two anti-glaucoma drugs in the study eye. Anti-glaucoma eye drops should be dosed at least 30 minutes before the investigational product dosing.

• Have poor posterior view due to dilation or media opacity that limits ability to do OCT, or photography.

• Have any clinically significant systemic disease or condition (e.g. hematological diseases) that, in the Investigator's opinion, may confound the trial results, pose a safety risk to the subject or preclude the subject from adhering to the protocol or completing the

--	---

	
trial per protocol, or instilling eye drops.
 

• Have had corneal refractive, laser or incisional surgery in the study eye within three months of Visit 1.

• Have a known history of alcohol and/or drug abuse.

• Have been exposed to an investigational drug or investigational medical device within 60 days prior to Visit 1.

• Be an employee of the site that is directly involved in the management, administration, or support of this study or be an immediate family member of the same.

--	---

## LIST OF ABBREVIATIONS AND DEFINITIONS OF TERMS

Abbreviation/Term	Definition
OTC	Over the counter
OU	Oculus Uterque (both eyes)
PP	Polypropylene
PP	Per Protocol
PRN	As Needed
QID	Four times daily
SAE	Serious Adverse Event
SAR	Suspected Adverse Reaction
SD-OCT	Spectral-Domain Optical Coherence Tomography
US	United States of America
VA	Visual Acuity
w/v	Weight to Volume

## 1 INTRODUCTION

Uveitis refers to a broad spectrum of ocular inflammatory diseases which are associated with both systemic infectious and non-infectious conditions. Non-infectious uveitis, a potentially blinding condition that is the fifth leading cause of visual loss in the developed world (third leading cause of preventable blindness), has been estimated to account for 10% of all visual impairment in the western world and 10–15% of cases of total blindness [Nussenblatt, 1990; Merida et al., 2015].

The inflammation associated with uveitis affects the uvea of the eye (iris, ciliary body and choroid) and it is characterized by an inflammatory process that may be acute, recurrent, chronic or acute-on-chronic. Untreated, recurrent bouts of uveitis eventually lead to tissue destruction from direct inflammation or from complications such as cataract, glaucoma and macular edema. Clinically, uveitis manifestations include pain, blurry vision, conjunctival hyperemia, anterior chamber cells, anterior chamber flare, fibrin deposition and corneal endothelial inflammatory precipitates.

Uveitis may affect either the anterior or the posterior segment or in the case of panuveitis, it affects the entire eye. Anterior uveitis, which specifically refers to uveitis in the anterior segment of the eye, is the most common and accounts for approximately 80% of non-infectious uveitis cases in the United States [Thorne et al., 2016].

The present clinical trial evaluates the treatment of non-infectious anterior uveitis with TRS01.

Topical corticosteroids represent first line treatment for both non-infectious anterior uveitis and postoperative inflammation [Kim et al., 2019]. The side effects associated with steroid use significantly limit prolonged treatment. The most common adverse effects of ocular steroids are cataract and elevated intraocular pressure (IOP) which can lead to steroid related glaucoma.

Given the limitations of steroid treatment, there is an unmet medical need for an effective anti-inflammatory drug that does not have an IOP-elevating effect or cause the formation of cataracts. Tarsius Pharma, Ltd. has developed a novel therapeutic approach for local prevention and treatment of ophthalmic inflammatory diseases. [REDACTED]

TRS is the active drug substance of TRS01 which is an [REDACTED] drug product candidate developed for topical ocular administration (eye drops). Pre-clinical studies have demonstrated the safety and tolerability of TRS01.

[REDACTED]

[REDACTED]

[REDACTED]

[REDACTED]

[REDACTED]

The GADOT 20/20 Trial is a Phase I/IIa randomized, double-masked, dose-ranging study to evaluate the safety and tolerability of TRS01 eye drops in subjects with active non-infectious anterior uveitis.

